Interpretation Training to Reduce Anxiety: Evaluating Technology-based Delivery Models and Methods to
Reduce Attrition

Study Protocol and Statistical Analysis Plan

NCT03498651

May 24, 2023

Web-Based Interpretation Bias Training to Reduce Anxiety: A Sequential, Multiple-Assignment, Randomized Trial

Metadata

Contributors

[name], [name], and [name]

Description

This is an initial pre-registration for a sequential, multiple assignment, randomized trial testing the target engagement and effectiveness of an online interpretation bias training intervention in a geographically diverse, anxious, treatment-seeking sample.

Registration Type

OSF Preregistration

Date Registered

December 2, 2020

Date Created

December 2, 2020

Study Information

Hypotheses

This sequential, multiple assignment, randomized trial (SMART) was pre-registered at clinicaltrials.gov (<https://clinicaltrials.gov/ct2/show/NCT03498651>) and was designed to test the target engagement and effectiveness of an online interpretation bias training intervention in a geographically diverse, anxious, treatment-seeking sample. Further, this study aims to investigate whether adding minimal human contact for participants at high risk of attrition improves intervention retention and treatment outcomes. Here we pre-register the following hypotheses:

Interpretation Bias and Anxiety Hypotheses

A cognitive style characterized by rigid, negative interpretations of ambiguous situations has been associated with anxiety-related pathology (Beard, 2011). Cognitive bias modification for interpretations (CBM-I) is an online cognitive training intervention that aims to reduce symptoms of anxiety by training individuals to interpret ambiguous situations less negatively (Hallion & Ruscio, 2011). We will test the effectiveness of the CBM-I intervention on measures of target engagement (i.e., interpretation bias) and measures of anxiety severity. We expect that

individuals assigned to all arms of the CBM-I treatment, as compared to those randomized to complete a series of psychoeducation tutorials, will show a greater increase in positive interpretation bias and a greater reduction in negative interpretation bias and anxiety symptoms from pre-treatment to post-treatment (where post-treatment is measured immediately following session 5). We also expect that treatment gains will be maintained for individuals assigned to CBM-I (vs. psychoeducation) at two-month follow-up. When comparing outcomes within the three CBM-I arms of the study, we expect the high-risk for attrition plus telecoaching group to show greater increases in positive interpretation bias and greater reductions in negative interpretation bias and anxiety symptoms compared to the high risk for attrition group who were not randomized to receive telecoaching. Comparisons between the low risk for attrition group and the high risk for attrition groups (with or without telecoaching) are of secondary interest and these hypotheses are non-directional.

Treatment Dropout Hypotheses

Online mental health interventions have long-been plagued by high user dropout (Eysenbach, 2005). Therefore, it is important to investigate whether adding minimal human contact (i.e., providing telecoaching) to participants identified as being at high risk for treatment dropout improves retention in this online intervention trial. We expect that CBM-I participants identified as being at high risk of treatment dropout who were randomized to receive a supplemental telecoaching intervention will drop out at a later session than high risk CBM-I participants who did not get randomized to the telecoaching intervention. Further, we expect that the three CBM-I arms of the trial will be associated with less attrition than the psychoeducation comparison group.

Notably, participants were not randomly assigned to their high- or low-risk status, so causal inference between the high and low risk CBM-I groups is unsupported by this SMART design. However, we expect that participants identified as being at high risk of treatment dropout but who did not receive the telecoaching intervention will show earlier treatment dropout than CBM-I participants identified as being at low risk for attrition. As a secondary analysis, we will also compare treatment dropout between low risk CBM-I participants and those high risk CBM-I participants who received the additional telecoaching intervention to test whether or not the supplementary telecoaching intervention appears to buffer against the risk of early dropout. However, this hypothesis is non-directional.

Design Plan

Study Type

Experiment - A researcher randomly assigns treatments to study subjects, this includes field or lab experiments. This is also known as an intervention experiment and includes randomized controlled trials.

Blinding

For studies that involve human subjects, they will not know the treatment group to which they have been assigned.

Is there any additional blinding in this study?

No response

Study Design

We recruited and enrolled 1746 anxious adults with access to a smartphone, computer, or tablet to participate in a “computer-based program to reduce anxiety symptoms.” Participants were eligible to participate if they scored at or above a 10 on the anxiety subscale of the Depression, Anxiety, and Stress Scale (DASS-AS; Lovibond & Lovibond, 1995), had access to an internet-enabled device, and were at least 18 years of age.

Enrolled participants who completed readiness rulers and demographics questions at pretreatment were randomly assigned to either complete five 15-minute cognitive bias modification for interpretations (CBM-I) training sessions with 40 scenarios per session or to a psychoeducation condition according to a 75:25 stratified randomization ratio schedule. Participants were instructed to complete one training session per week over the course of five weeks and were instructed to complete these online training sessions using their preferred internet-enabled device (i.e., participants could opt to use multiple devices or to use the same device throughout the five-week training).

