Further, to code treatment condition for the four treatment arms in line with methods described by Lu and colleagues (2015) and Nahum-Shani and colleagues (2019), we will create a label of contrast codes for each of the two stages of the intervention. We elect to use contrast coding (1/-1) as opposed to dummy coding (0/1) so that we will be able to directly compare outcomes tests of regression coefficients to tests of main effects (see Collins, 2018; Myers, Well, & Lorch, 2010). Because there are two intervention stages by design (i.e., two sequential randomization decision points), we will let (a1, a2) denote the different contrast codes we'll test between treatment arms at both randomization stages.

Let a1 = -1 for participants initially randomized to psychoeducation and let a1 = 1 for participants initially randomized to CBM-I.

Given that there are multiple comparisons of interest following the second randomization point, we specify four different sets of a2 contrast values. These values are delineated in Pre-registration Table 2 such that a2,1 compares the average of all three CBM-I arms to the psychoeducation arm, a2,2 compares the high risk CBM plus telecoaching arm to the high risk CBM with no telecoaching added arm, a2,3 compares the high risk CBM plus telecoaching arm to the low risk CBM arm, and a2,4 compares the high risk CBM with no telecoaching added arm to the low risk CBM arm.

Pre-Registration Table 2

Treatment Arm	a_1	$a_{2,1}$	$a_{2,2}$	$a_{2,3}$	$a_{2,4}$
Low Risk CBM-I Throughout	1	1	0	-1	-1
High Risk CBM-I + Telecoaching	1	1	1	1	0
High Risk CBM-I No Telecoaching Added	1	1	-1	0	1
Psychoeducation throughout	-1	-1	0	0	0

The proposed model equation is provided in Pre-Registration Equation Set 1.

Pre-Registration Equation Set 1

$$Lvl2 : \beta_{0i} = \gamma_{00} + \gamma_{01}Z_{SES} + \gamma_{02}Z_{age} + \gamma_{03}Z_{SES}Z_{age} + \mu_{0i}$$

$$Lvl2 : \beta_{1i} = \gamma_{10} + \gamma_{11}a_1 + \gamma_{12}Z_{SES} + \gamma_{13}Z_{age} + \gamma_{14}a_1Z_{SES} + \gamma_{15}a_1Z_{age} + \gamma_{16}Z_{SES}Z_{age} + \gamma_{17}a_1Z_{SES}Z_{age} + \mu_{1i}$$

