$$Lvl1 : Y_{ij} = \beta_{0i} + \beta_{1i}S_{1j} + \beta_{2i}S_{2j} + e_{ij}$$

Where Y_{ij} is the continuous outcome variable for person i at time j where $i = 1, 2, \dots, N$ and $j = 1, 2, \dots, 6$ (for pre-treatment, session 1, ..., session 5); β_{0i} through β_{2i} values are the random effects; S_{1j} is time at the first stage of the clinical trial (pre-treatment to re-randomization point after session); S_{2j} is time at the second stage of the clinical trial (session 1 to session 5); α_1 specifies the treatment arm contrast comparison after the initial randomization; α_2 specifies the treatment arm contrast comparison after re-randomization; Z_{SES} is a control variable for participant socioeconomic status; and Z_{age} is a control variable for participant age.

Note that for simplicity, the above equations only show one α_2 value. Since our four contrasts are not orthogonal, we will attempt to include all four α_2 contrasts in one `rjags` model for each outcome variable of interest. If this added complexity prevents model convergence, we will run four separate models, each specifying one of the four α_2 contrast codes.

Estimands. We have identified four estimands of interest upon which to interpret our treatment dropout hypotheses: Study arm differences in (1) average likelihood to have dropped out during or before session 5 training (i.e., time-specific outcome of primary interest), (2) average likelihood to have dropped out during or before session 2 training (i.e., time-specific outcome of secondary interest), (3) average likelihood to have dropped out during or before session 3 training (i.e., time-specific outcome of secondary interest); and (4) average likelihood to have dropped out during or before session 4 training (i.e., time-specific outcome of secondary interest).

- [Pre-Registration Table 1.png](#)
- [Pre-Registration Table 2.png](#)
- [Pre-Registration Equation Set 1.png](#)
- [Pre-Registration Table 3.png](#)
- [Pre-Registration Equation Set 2.png](#)

Transformations

As stated above, we will center time (S1) at zero for all longitudinal models such that the pre-intervention assessment points for all participants, regardless of the date of their initial assessment, will be set to 0.

We will mean center any continuous baseline covariates (e.g., SES).

Inference Criteria

We will make statistical inferences according to obtained HPD 95% Credible Intervals.

Data Exclusion

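### The question whether telecoaching buffers against dropout is given to the coached-high-risk versus low-risk comparison, which mixes the non-randomized risk gap with the coaching effect and cannot answer it in either direction

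*Combined protocol and SAP*

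**What the plan says.** The section Treatment Dropout Hypotheses contains three comparisons among the CBM-I arms.

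- Coached versus uncoached high risk. This is directional: coached participants "will drop out at a later session than high risk CBM-I participants who did not get randomized to the telecoaching intervention". The Statistical Models section codes it: "a2,2 compares the high risk CBM plus telecoaching arm to the high risk CBM with no telecoaching added arm".
- Uncoached high risk versus low risk. Earlier dropout is expected in the uncoached high-risk arm. This is coded a2,4.
- Low risk versus coached high risk. As a secondary analysis the plan will "compare treatment dropout between low risk CBM-I participants and those high risk CBM-I participants who received the additional telecoaching intervention", in order to "test whether or not the supplementary telecoaching intervention appears to buffer against the risk of early dropout". The paragraph ends: "However, this hypothesis is non-directional". The coding is "a2,3 compares the high risk CBM plus telecoaching arm to the low risk CBM arm".

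The paragraph holding the last two comparisons opens by noting that risk status was not randomized, so that "causal inference between the high and low risk CBM-I groups is unsupported by this SMART design". The only decision criterion is under Inference Criteria: "We will make statistical inferences according to obtained HPD 95% Credible Intervals". No equivalence margin is given, and nothing says which a2,3 result would count as buffering.

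**The concern.** To say that coaching buffers is to say that high-risk participants drop out less with coaching than they would have without it. The matching comparison is coached against uncoached high risk, which Stage 2 randomized. The plan attaches the question to a different comparison, one that contains no uncoached high-risk participants.

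How far coached participants end up from low-risk participants depends on two things: what coaching did, and how far apart the algorithm placed the two risk groups to begin with. If the algorithm separates weakly, coached and low-risk participants look alike even when coaching is inert. If it separates strongly, coached participants still look worse even when coaching has helped a great deal. A report that follows the text could attribute a benefit to coaching that it did not have, or deny one that it did. Improving retention among high-risk participants is a stated aim of the trial, so this sentence would be read with interest.

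**Working it through.** **The plan's own figure.** There is none for this contrast. Sample Size Rationale concerns a main effect in a 2 x 3 ANOVA.

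**1. What a2,3 measures.** Let C, H and L be dropout in the coached high-risk, uncoached high-risk and low-risk arms. Pre-Registration Table 2 gives:

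| Arm | a2,2 | a2,4 | a2,2 + a2,4 | a2,3 |
|---|---|---|---|---|
| Low risk | 0 | -1 | -1 | -1 |
| High risk, coached | 1 | 0 | 1 | 1 |
| High risk, uncoached | -1 | 1 | 0 | 0 |
| Psychoeducation | 0 | 0 | 0 | 0 |

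So a2,3 = a2,4 + a2,2 in every row, that is, (C - L) = (H - L) + (C - H). The first term is the non-randomized risk gap and the second is the randomized coaching effect. The identity holds on the probability or the logit scale, and for Bayesian or frequentist estimates. One value of C - L is compatible with any coaching effect, depending on H - L.

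**2. Inputs for the illustration.** Sample Size gives 282 coached, 265 uncoached and 288 low-risk participants. Dropout by arm is not stated. Pooled dropout is 1 - 559/1075 = 48%, if all 559 completers belong to the 1075 analyzed. The arm rates below are assumptions placed around that figure. A two-sided 5% two-proportion test stands in for the 95% HPD interval.

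**3. Formula.** For arms with rates p1 > p2 and difference d, let s0 be the pooled standard error and s1 the unpooled one. Then P(arm 1 significantly higher) = Phi[(d - 1.96 s0)/s1].

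**4. Coaching has no effect (C = H = 50%).**

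- L = 45%: s0 = 0.0418 and s1 = 0.0418, so (0.05 - 0.0820)/0.0418 = -0.77, giving 22%. C and L are not distinguished in about 78% of trials.
- L = 40%: s0 = 0.0417 and s1 = 0.0415, so (0.10 - 0.0817)/0.0415 = 0.44, giving 67%. They are not distinguished in about 33%.
- The randomized contrast a2,2 shows a false benefit in 2.5%, whatever L is.

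**5. Coaching works (H = 60%, C = 45%, L = 30%).**

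- a2,3: s0 = 0.0405 and s1 = 0.0401, so (0.15 - 0.0795)/0.0401 = 1.76. Coached participants are significantly worse than low-risk in 96% of trials (68% if L = 35%).
- a2,2: s0 = 0.0427 and s1 = 0.0422, so (0.15 - 0.0838)/0.0422 = 1.57. The benefit is detected in 94%.

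**6. Reading a2,3 together with a2,4.** Take as the buffering pattern that H is significantly worse than L while C does not differ from L. With no coaching effect (C = H = 50%; 200,000 simulated trials per row):

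| L | Pattern appears | a2,2 shows false benefit |
|---|---|---|
| 45% | 11.8% | 2.5% |
| 42% | 16.0% | 2.4% |
| 40% | 14.5% | 2.5% |
| 35% | 3.5% | 2.4% |

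The joint reading helps, but for gaps of 5 to 10 points it still yields a spurious pattern in about 12% to 16% of trials.

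**The case against.** The strongest reply is that the plan already tests coaching properly. The directional hypothesis on coached versus uncoached high-risk participants comes first in the section, rests on randomization and has its own code. The a2,3 comparison is secondary, non-directional, worded with *appears to*, and introduced by a warning against causal inference across risk groups. All of this stands. A reader might infer that the trial has no valid test of telecoaching on dropout; the documents show otherwise.

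A reader might also infer that the plan intends to call a null a2,3 result buffering. It does not say so: it gives the 95% HPD criterion and leaves the interpretation open. The 78% and 33% above are therefore how often a null would occur with inert coaching, not error rates of a stated rule. At a 5-point gap, moreover, a2,4 would itself reach significance in only about 22% of trials, so there would often be no demonstrated excess to buffer. Since the uncoached comparison stands in the sentence just before, reading the two together is natural, and that lowers the rate to about 12% to 16%.

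What remains is that the text names this comparison as the test of buffering and never passes the conclusion to a2,2. The non-causal caveat is a fair warning, but it leaves a claim about what coaching does attached to a comparison that the same paragraph says cannot support one.

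**Conclusion.** Wrong as written, of minor severity. The buffering conclusion is tied to a contrast that adds the risk gap to the coaching effect, so neither result of that contrast settles the question. This rests on the coding table alone and needs no assumption.

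The percentages are illustrations only. They use assumed dropout rates by arm and simple two-proportion tests in place of the planned Bayesian multilevel logistic model with covariates, so they show direction and rough scale and will not carry over exactly. The randomized hypothesis on telecoaching is unaffected.

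**What to change.** In Treatment Dropout Hypotheses:

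- Base any conclusion that telecoaching buffers against dropout on a2,2: coached versus uncoached high risk, with the 95% HPD interval excluding zero in favour of coaching.
- Relabel a2,3 as a descriptive estimate of the gap remaining between coached high-risk and low-risk participants, reported with its interval.
- State that an a2,3 interval including zero is not evidence of buffering, and that one excluding zero is not evidence against it.

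A ratio for the share of the risk gap closed may look attractive, but I would not add it. Its denominator is the non-randomized gap. The four a2 codes have rank 3, so they cannot be separately identified when entered together, and the fallback of one model per contrast gives no joint posterior for the ratio.

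The cost is a few sentences; no new data or model is needed. The limit to accept is precision: on the same approximation, a2,2 has about 65% power for a 10-point fall (60% to 50%), so an a2,2 interval including zero should not be reported as showing that coaching has no effect.

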The above randomization scheme was specified to ultimately yield equal cell sizes for each of the four conditions (i.e., 25% of randomized subjects in each). However, as of 10/28/2019, the four cell sizes were imbalanced (ranging from 15.9% to 25%) due to a large number of CBM-I subjects not completing Session 1 after Stage 1 randomization to the CBM-I arm of the intervention. Importantly, completed Session 1 measures were needed for the attrition algorithm to be able to classify CBM-I subjects as high or low risk of dropout before Stage 2 randomization could be applied to high risk subjects. Thus, to reduce the imbalance in the number of subjects randomly assigned to each of the four groups across both stages of randomization, we changed the allocation at Stage 1 randomization on 10/31/2019 from 25% Psychoeducation and 75% to CBM-I to 10% and 90%, respectively.

Sampling Plan

Existing Data

Registration prior to analysis of the data

Explanation of Existing Data

We registered the overall project and identified primary outcomes at clinicaltrials.gov (<https://clinicaltrials.gov/ct2/show/NCT03498651>) prior to data collection. However, this pre-registration through OSF is occurring after data collection but prior to any data analysis. This pre-registration represents the first set of substantive analyses proposed in this dataset. To date, these data have only been viewed by members of the overall data collection team to ensure accurate and representative enrollment of participants (i.e., that we are succeeding in recruiting a diverse sample). We also regularly reported attrition updates by blinded condition to an independent safety monitor throughout the data collection process and completed blind data integrity checks (i.e., to catch duplicate entries). Data cleaning is currently ongoing by members of the team who are not involved in hypothesis generation.

Data Collection Procedures

Intervention sessions were administered and data were collected through the established MindTrails website. Enrollment was open to an international sample of anxious adults (inclusion

criteria listed in the study design section of this registration). Participants were recruited through postings on online newsletters, research websites, mental health forums, Craigslist, social media (e.g., Facebook, Instagram, Twitter, Reddit), and UVA student group listservs; flyers posted in the Charlottesville community and at UVA and other nearby universities and community colleges; news sources (e.g., articles, radio interviews, podcasts); and Google Ads. In addition, to improve recruitment of underrepresented groups, we sent emails to a market research firm's database of participants who self-identified with anxiety or depression and as Black/African American, Hispanic/Latinx, or Asian; we also posted in an online newsletter for multicultural student services at UVA. Note that participants may have presented to the Mindtrails website starting on 3/12/2020 due to concerns over the developing COVID-19 pandemic. Although future analyses may choose to test whether these participants interacted with the intervention differently than did pre-COVID participants, we elect to combine all participants in this initial investigation of the major aims of this clinical trial.

Per protocol, after enrollment and informed consent was obtained, each participant completed a pre-treatment assessment battery, one training session per week over the course of five weeks, comprehensive assessment batteries immediately following training sessions 3 and 5, and a follow-up assessment battery two months after training ended. Participants also completed a shorter schedule of assessments after training sessions 1, 2, and 4 to reduce participant burden.

Participants were compensated via e-gift cards according to the following payment schedule. Participants were awarded \$5 per assessment battery completed at pre-treatment, after session 3, and after session 5. Participants were further awarded \$10 for completing the 2-month follow-up assessment, amounting to a total possible compensation of \$25 in e-gift cards distributed by Tango Cards.

No files selected

Sample Size

Per protocol, we planned to recruit and enroll 1,000 highly anxious individuals and sequentially employ a series of weighted randomization rules to achieve four treatment arms (i.e., four study conditions) of approximately equal weight (approximately 250 participants per group). Data collection is now complete and we enrolled 1746 participants in total. Of these, 1238 started the first training session and are considered intent to treat (ITT). At Stage 1 randomization, 984 ITT participants were assigned to CBM-I, and 254 ITT participants were assigned to psychoeducation. 1075 ITT participants completed assessments immediately following the first training session (835 in CBM-I and 240 in psychoeducation) and are included in our primary analyses. The 835 CBM-I completers of the session 1 assessments were classified as higher ($n = 547$) or lower ($n = 288$) risk of study dropout, whereas the 149 CBM-I participants who did not complete the session 1 assessments were not able to be classified as higher or lower risk of study dropout. Of the 547 CBM-I participants classified as higher risk of study dropout, at Stage 2 randomization 282 were assigned to receive coaching and 265 were assigned to no change. In total, 559 of the 1238 ITT participants completed five training sessions and are deemed treatment completers.

Sample Size Rationale

Prior to data collection, we conducted an analysis of variance (ANOVA) to estimate the sample size needed to test main effects of delivery methods (i.e., phone vs. computer), human contact, and their interaction according to a 2 (phone vs. computer) x 3 (high risk: TeleCoach, high risk: continued CBM only, low risk: continued CBM only) design. While we ultimately decided to not randomize participants to CBM-I delivery platform (to prioritize participant preference to maximize engagement and minimize burden), our initial power analysis assumed small to medium effects for this 2x3 design. In this power analysis, we elected to be conservative due to the SMART design yielding unbalanced cell sizes. Further, given that the second stage of randomization is based on performance in the earlier stage, we were unable to determine what an effect size might be in advance. With our assumed effect size ($d = .35$, $f = .175$), to have 80% power, we would need $n = 240$ to detect a main effect. However, given that we expected high rates of attrition, we assumed a 66% dropout rate (based on previous attrition rates on our MindTrails cite), so we multiplied $n = 240$ by 3 [i.e., $1/1-.66$], resulting in $N = 720$. For the psychoeducation comparison condition, we elected to match the sample size to the expected final cell size for the three other conditions (i.e., $n = 120$). We did not scale up the condition sample size given the SMART design does not split the control condition in a second stage of randomization.

Stopping Rule

We stopped data collection based on a selected date. Data collection began on 3/18/2019. We analyzed data collected through 11/27/2020.

Variables

Manipulated Variables

There were two stages of randomization throughout the SMART (described elsewhere in this pre-registration).

No files selected

Measured Variables

Interpretation Bias (Target Engagement)

1) Recognition Ratings for Measuring Change in Interpretation Bias (modified from Matthews & Mackintosh, 2000). To measure negative and positive interpretation bias, participants were asked to complete the recognition ratings measure (modified from Matthews & Mackintosh, 2000) at pre-intervention, after session 3, after session 5, and at the 2-month follow-up. Participants were presented with nine ambiguous stories and were asked to imagine themselves in each of those nine situations. The final word of each story was presented as a word fragment and participants were asked to complete the final word to disambiguate the scenario. Participants were then asked to complete a comprehension question tied to each story's

resolution. After completing all nine stories, participants were presented with the title of each story, four alternative disambiguated interpretations per story, and were asked to rate how similar each of the four interpretations were to the original story's resolution using a scale ranging from 0 ("very different") to 3 ("very similar"). Participants also had the option to select Prefer Not to Answer. Two of the disambiguated interpretations provided per story were threat-related (one negative, one positive/benign) and two were threat-unrelated (one negative, one positive/benign). Endorsements of threat-relevant negative disambiguated interpretations are averaged across all nine stories to compute the negative interpretation bias score, where higher scores reflect a greater negative interpretation style. Endorsements of threat-relevant positive/benign disambiguated interpretations are averaged across the nine stories to derive the positive interpretation bias score, where higher scores reflect a greater positive interpretation style.

2) Brief Body Sensations Interpretations Questionnaire (BBSIQ; modified from Clark et al., 1997). To measure negative and positive interpretation bias using an approach less tied to the intervention's procedure, participants were asked to complete the Brief Body Sensations Interpretations Questionnaire (BBSIQ; modified from Clark et al., 1997) at pre-intervention, after session 3, after session 5, and at the 2-month follow-up. To complete the BBSIQ, participants were presented with 14 potentially threatening, ambiguous events and are asked to rate the extent to which they believed three alternative explanations for why the event might have occurred (where two explanations are benign and one explanation is anxiety-congruent) using a 0 ("not at all likely") to 4 ("extremely likely") Likert scale. Participants also had the option to select Prefer Not to Answer. The negative interpretation bias score is computed by averaging the likelihood ratings for all anxiety-congruent explanations, such that higher scores reflect a greater negative interpretation style, whereas the positive interpretation bias score is computed by averaging the likelihood ratings for all benign explanations, such that higher scores reflect a greater positive interpretation style.

Anxiety Symptoms

1) Overall Anxiety Severity and Impairment Scale (OASIS; adapted from Norman, Cissell, Means-Christensen, & Stein, 2006). To measure subjective evaluations of the frequency and severity of anxiety, avoidance, and associated impairment, participants completed the five-item OASIS (Norman et al., 2006). All items are rated on a scale of 0 (lowest impairment/severity) to 4 (highest impairment/severity). Participants also had the option to select Prefer Not to Answer. The OASIS was assessed at all time points (pre-intervention, after all five sessions, and at two-month follow-up).

2) Depression, Anxiety, Stress Scales-Short Form - Anxiety Subscale (DASS-AS; adapted from Lovibond & Lovibond, 1995). To assess eligibility to enroll in the study and to measure participants' subjective evaluations of the frequency of their anxiety symptoms since their last training session, participants completed the seven-item DASS-AS using the response scale 0 ("not at all") to 3 ("most of the time"), where higher scores indicate greater symptom severity. Participants also had the option to select Prefer Not to Answer. Participants completed this questionnaire at pre-screener, after session 3, after session 5, and at 2-month follow-up.

No files selected

Indices

No response

No files selected

Analysis Plan

Statistical Models

Models Testing Interpretation Bias and Anxiety Symptom Hypotheses

To assess the impact of different treatment arms on interpretation bias and anxiety symptom outcomes, we will run a series of multilevel models estimated in the Bayesian framework using the rjags package in R. Due to the repeated outcome monitoring structure of this clinical trial, assessment points will be nested within individual participants. We will control for socioeconomic status and age in all models given previous evidence that these demographic characteristics are associated with differential treatment responses to CBM-I. To our knowledge, this will be the first Bayesian test of CBM-I treatment effects and is also the first CBM-I SMART design. As such, we will use uninformative priors in these estimations.

Due to the study's SMART design, we will employ a piecewise linear function to model time. Doing so will allow us to minimize the bias that a simple linear mean trajectory would otherwise impose by not accounting for the possible deflection points at the time of re-randomization (Nahum-Shani et al., 2019). In a piecewise linear regression model, a separate line segment can be fit for different intervals over the course of the study, with the boundary for the time intervals forming a transition point, such as from one treatment stage to another. In the current study, we have three stages of interest: the first stage (S1) of the clinical trial (pre-treatment to re-randomization point after session 1); the second stage (S2) of the clinical trial (session 2 to session 5); and the third, or follow-up, stage (S3) of the clinical trial (session 5 until two months later). With a piecewise regression model, the linear trend in the outcome during the first stage can be allowed to vary from the linear trend during the second and third stages, and to be impacted by different variables. We will assume the same intercept for all four treatment arms because, by design, treatment arms are not expected to differ at baseline. We will assume that the marginal mean trajectory between the 3 CBM-I treatment arms will be equivalent until re-randomization occurs for the high-risk CBM-I participants following the first session. Given that longitudinal modeling of SMART data must accommodate features of the SMART design itself (Nahum-Shani et al., 2019), we will code time using three variables constructed in the manner outlined in Pre-registration Table 1.

Pre-Registration Table 1

Time	S₁	S₂	S₃
Pre-intervention	0	0	0
Session 1	1	0	0
Session 2	1	1	0
Session 3	1	2	0
Session 4	1	3	0
Session 5	1	4	0
2-month Follow-up	1	4	1

Further, to code treatment condition for the four treatment arms in line with methods described by Lu and colleagues (2015) and Nahum-Shani and colleagues (2019), we will create a label of contrast codes for each of the two stages of the intervention. We elect to use contrast coding (1/-1) as opposed to dummy coding (0/1) so that we will be able to directly compare outcomes tests of regression coefficients to tests of main effects (see Collins, 2018; Myers, Well, & Lorch, 2010). Because there are two intervention stages by design (i.e., two sequential randomization decision points), we will let (a1, a2) denote the different contrast codes we'll test between treatment arms at both randomization stages.

Let a1 = -1 for participants initially randomized to psychoeducation and let a1 = 1 for participants initially randomized to CBM-I.

Given that there are multiple comparisons of interest following the second randomization point, we specify four different sets of a2 contrast values. These values are delineated in Pre-registration Table 2 such that a2,1 compares the average of all three CBM-I arms to the psychoeducation arm, a2,2 compares the high risk CBM plus telecoaching arm to the high risk CBM with no telecoaching added arm, a2,3 compares the high risk CBM plus telecoaching arm to the low risk CBM arm, and a2,4 compares the high risk CBM with no telecoaching added arm to the low risk CBM arm.

Pre-Registration Table 2

Treatment Arm	a_1	$a_{2,1}$	$a_{2,2}$	$a_{2,3}$	$a_{2,4}$
Low Risk CBM-I Throughout	1	1	0	-1	-1
High Risk CBM-I + Telecoaching	1	1	1	1	0
High Risk CBM-I No Telecoaching Added	1	1	-1	0	1
Psychoeducation throughout	-1	-1	0	0	0

The proposed model equation is provided in Pre-Registration Equation Set 1.

Pre-Registration Equation Set 1

$$Lvl2 : \beta_{0i} = \gamma_{00} + \gamma_{01}Z_{SES} + \gamma_{02}Z_{age} + \gamma_{03}Z_{SES}Z_{age} + \mu_{0i}$$

$$Lvl2 : \beta_{1i} = \gamma_{10} + \gamma_{11}a_1 + \gamma_{12}Z_{SES} + \gamma_{13}Z_{age} + \gamma_{14}a_1Z_{SES} + \gamma_{15}a_1Z_{age} + \gamma_{16}Z_{SES}Z_{age} + \gamma_{17}a_1Z_{SES}Z_{age} + \mu_{1i}$$

$$Lvl2 : \beta_{2i} = \gamma_{20} + \gamma_{21}a_1 + \gamma_{22}a_2 + \gamma_{23}Z_{SES} + \gamma_{24}Z_{age} + \gamma_{25}a_1a_2 + \gamma_{26}a_1Z_{SES} + \gamma_{27}a_1Z_{age} + \gamma_{28}a_2Z_{SES} + \gamma_{29}a_2Z_{age} + \gamma_{210}Z_{SES}Z_{age} + \gamma_{211}a_1a_2Z_{SES} + \gamma_{212}a_1a_2Z_{age} + \gamma_{213}a_1Z_{SES}Z_{age} + \gamma_{214}a_2Z_{SES}Z_{age} + \gamma_{215}a_1a_2Z_{SES}Z_{age} + \mu_{2i}$$

$$Lvl2 : \beta_{3i} = \gamma_{30} + \gamma_{31}a_1 + \gamma_{32}a_2 + \gamma_{33}Z_{SES} + \gamma_{34}Z_{age} + \gamma_{35}a_1a_2 + \gamma_{36}a_1Z_{SES} + \gamma_{37}a_1Z_{age} + \gamma_{38}a_2Z_{SES} + \gamma_{39}a_2Z_{age} + \gamma_{310}Z_{SES}Z_{age} + \gamma_{311}a_1a_2Z_{SES} + \gamma_{312}a_1a_2Z_{age} + \gamma_{313}a_1Z_{SES}Z_{age} + \gamma_{314}a_2Z_{SES}Z_{age} + \gamma_{315}a_1a_2Z_{SES}Z_{age} + \mu_{3i}$$

$$Lvl1 : Y_{ij} = \beta_{0i} + \beta_{1i}S_{1j} + \beta_{2i}S_{2j} + \beta_{3i}S_{3j} + e_{ij}$$

Where Y_{ij} is the continuous outcome variable for person i at time j where $i = 1, 2, \dots, N$ and $j = 1, 2, \dots, 7$ (for pre-treatment, session 1, ..., 2-month follow-up); β_{0i} through β_{3i} values are the random effects; S_{1j} is time at the first stage of the clinical trial (pre-treatment to re-randomization point after session 1); S_{2j} is time at the second stage of the clinical trial (session 1 to session 5); S_{3j} is time at the third, or follow-up, stage of the clinical trial (session 5 until two months later); a_1 specifies the treatment arm contrast comparison after the initial randomization; a_2 specifies the treatment arm contrast comparison after re-randomization; Z_{SES} is a control variable for participant socioeconomic status; and Z_{age} is a control variable for participant age.

Note that for simplicity, the above equations only show one a_2 value. Since our four contrasts are not orthogonal, we will attempt to include all four a_2 contrasts in one $rxjags$ model for each outcome variable of interest. If this added complexity prevents model convergence, we will run four separate models, each specifying one of the four a_2 contrast codes.

Estimands. We have identified three estimands of interest upon which to interpret our interpretation bias and anxiety hypotheses: Study arm differences in (1) average outcomes at the end of the session 5 and at 2-month follow-up (i.e., time-specific outcomes); (3) rates of change

